HBsAg	Hepatitis B surface antigen
HBV	Hepatitis B virus
HCV	Hepatitis C virus
HCV Ab	Hepatitis C antibody
HDL	High-density lipoprotein
HIPAA	Health Insurance Portability and Accountability Act
HIV	Human immunodeficiency virus
HIV Ab	Human immunodeficiency virus antibody
HR	Heart rate
ICH	International Conference on Harmonization
ICH E6 R2	International Council for Harmonisation of Technical Requirements for Pharmaceuticals for Human Use Guidance for Industry, Good Clinical Practice: Consolidated Guidance, Revision 2
ICMJE	International Committee of Medical Journal Editors
ICSR	Individual Case Safety Report
IEC	Independent Ethics Committee
IgA	Immunoglobulin A
IMP	Investigational medical product
IND	Investigational New Drug Application
IRB	Investigational Review Board
IRT	Interactive response technology
ITT	Intent-to-treat
IV	Intravenous
LDH	Lactate dehydrogenase
LDL	Low-density lipoprotein
LV	Left ventricular
MCI	Mild cognitive impairment
MDRD	Modification in diet in renal disease
MDS-PD	Movement Disorder Society's Clinical Diagnostic Criteria for Parkinson's Disease
MDS-UPDRS	Movement Disorder Society's Unified Parkinson's Disease Rating Scale
MedDRA	Medical Dictionary for Regulatory Activities
MHIS	Modified Hachinski Ischemic Scale
MoCA	Montreal Cognitive Assessment
MRI	Magnetic resonance imaging
NODscid	Non-obese diabetic severe combined immunodeficiency
NSG	NODscid gamma
PD	Parkinson's disease
PDD	Parkinson's disease dementia
PD-MCI	Parkinson's disease with mild cognitive impairment
PDQ-39	Parkinson's Disease Quality of Life Questionnaire-39
PT	Preferred Term
PT/INR	Prothrombin time/international normalized ratio

PTT	Prothrombin time
RBC	Red blood cell
RR	Respiration rate
SAE	Serious adverse event
SAP	Statistical Analytical Plan
SBP	Systolic blood pressure
SE-ADL	Schwab and England Activities of Daily Living
SOC	System Organ Class
SOP	Standard operating procedure
S-STS	Sheehan-Suicidality Tracking Scale
SUSAR	Suspected unexpected serious adverse reaction
TEAE	Treatment emergent adverse event
tf-fMRI	Task-free functional magnetic resonance imaging
TGA	Therapeutic Goods Administration
TSH	Thyroid-stimulating hormone
UPCR	Urine protein-to-creatinine ratio
US	United States
vCJD	Variant Creutzfeldt-Jakob disease
WBC	White blood cell
WOCBP	Women of childbearing potential

LIST OF DEFINITIONS

- Agree to assume responsibility for the proper conduct of the study at this site, including complying with current relevant versions of the United States (US) Food and Drug Administration (FDA) regulations, the International Council for Harmonisation of Technical Requirements for Pharmaceuticals for Human Use (ICH) Good Clinical Practice (GCP) guidelines, the Declaration of Helsinki, and all applicable rules, regulations, and federal, state, and local laws relating to the conduct of clinical studies and the protection of human subjects.
- Agree not to implement deviations from or changes to the protocol or protocol amendments without agreement from the Sponsor and prior submission to and written approval (where required) from the Institutional Review Board (IRB) or Independent Ethics Committee (IEC), except when necessary to eliminate an immediate hazard to the subjects, or for administrative aspects of the study (where permitted by all applicable regulatory requirements).
- Agree to onsite monitoring of all source documents by Alkahest, Inc. or designee and to onsite inspection of source documents by appropriate regulatory authorities, including but not limited to the FDA, local governing regulatory bodies, and IRB/IEC inspectors.

Investigator's Signature

Date

Print Name

PROTOCOL SUMMARY

Title: A Randomized, Double-Blind, Placebo-Controlled Study to Assess the Safety and Tolerability of GRF6021 Infusions in Subjects with Parkinson's Disease and Cognitive Impairment

Précis: This is a randomized, double-blind, placebo-controlled study to assess the safety and tolerability of GRF6021, a [REDACTED] human [REDACTED] fraction, administered by intravenous (IV) infusion to subjects with Parkinson's disease (PD) and cognitive impairment.

The study consists of approximately 90 subjects who will be randomized in a 2:1 ratio to active treatment (approximately 60 subjects) or placebo (approximately 30 subjects). Subjects will receive one infusion per day of active or placebo treatment for 5 consecutive days during week 1 and week 13. The study duration for the subjects will be approximately 7 months.

Each infusion will have a duration of approximately [REDACTED] with a maximum of [REDACTED]. The infusion of active and placebo agents will be identical to maintain blinding. The following measures will be taken to ensure adequate allocation concealment during infusions: blinding of subjects, trial partners, study coordinators, physicians, and cognitive/motor test administrators to treatment allocation; use of blinded Outcomes Assessors and unblinded Infusion Nurses; and measures to block view of the infusion setup to avoid unblinding.

All subjects will undergo a screening visit, including a magnetic resonance imaging (MRI) scan, baseline visit, two treatment periods, follow-up visits, and an end-of-study/early-termination visit. During each 5-day treatment period, administration of GRF6021/placebo can occur in an inpatient/hospital setting or in outpatient infusion centers or equivalent facilities with appropriate medical personnel. All infusions must be performed by adequately trained personnel under the supervision of the investigator. Safety and tolerability assessments will occur at every visit. Neurocognitive and motor assessments will be performed at baseline and at periodic visits following dosing. Subjects who provide explicit consent to undergo a second, optional MRI scan will have an additional MRI scan at Visit 16 to assess for changes from screening.

Objectives: The primary objective of the study is to assess the safety and tolerability of an infusion dosing regimen of GRF6021 in subjects with PD and cognitive impairment. As a secondary objective, the study will assess the potential effects of GRF6021 on cognition and motor function as well as changes from baseline in clinical laboratory parameters, vital signs, body weight, and the Sheehan-Suicidality Tracking Scale (S-STSS). The exploratory objectives include serial compositional analysis of plasma to identify

specific biomarkers associated with cognitive and motor function and/or indicators of disease progression, and changes on MRI (in consenting subjects).

Endpoints:

Primary Endpoint:

- Incidence of treatment-emergent adverse events (TEAEs) and serious adverse events (SAEs) identified by the Medical Dictionary for Regulatory Activities (MedDRA) preferred term (PT) and grouped by MedDRA System Organ Class (SOC).

Secondary Efficacy Endpoints:

- Change from baseline in the Montreal Cognitive Assessment (MoCA).
- Change from baseline in Continuity and Power of Attention, Working Memory, and Episodic Memory on the Cognitive Drug Research Computerized Cognition Battery (CDR-CCB).
- Change from baseline in Delis-Kaplan Executive Function System (D-KEFS) Verbal Fluency.
- Change from baseline in the Movement Disorder Society’s Unified Parkinson’s Disease Rating Scale (MDS-UPDRS) 1, 2, 3, and total score.
- Change from baseline in the Schwab and England Activities of Daily Living (SE-ADL) Scale.
- Change from baseline in the Clinical Impression of Severity Index – PD (CISI-PD).
- Change from baseline in the PD Quality of Life Questionnaire-39 (PDQ-39).
- Change from baseline in the Geriatric Depression Scale-15 (GDS-15).
- Change from baseline in the digital clock drawing test (dCDT).

Secondary Safety Endpoints:

- Change from baseline in clinical laboratory parameters.
- Change from baseline in vital sign measurements.
- Change from baseline in body weight.
- Change from baseline in the S-STS.

Exploratory Endpoints:

- Proteomic assessment of plasma for investigation of study-related biomarkers.
- Change from baseline in various MRI assessments (in consenting subjects).

Population:

Approximately 90 subjects between 40 and 85 years of age with a diagnosis of either PD with mild cognitive impairment (PD-MCI) or PD with dementia (PDD). Assuming a drop-out rate of 25%, enrollment at this level

will yield approximately 68 evaluable subjects.

Phase: 2

Number of Sites: Up to 40 sites in the US and ex-US

Description of Study

Agent: GRF6021: A [REDACTED] human [REDACTED] fraction for IV infusion

[figure not shown]
Description of
Placebo Control

Agent: 0.9% sodium chloride injection (saline)

Study Duration: Approximately 24 months

Subject Duration: Approximately 7 months

SCHEMATIC OF STUDY DESIGN

1.2 STUDY ORGANIZATION

The name and contact information of the responsible party and individuals involved with the study (e.g., investigator(s), Sponsor’s medical expert and study monitor, Sponsor’s representative(s), laboratories, steering committees, and oversight committees (including IECs and IRBs, as applicable) will be maintained by the Sponsor, or their designee, and provided to the investigator.

2 INTRODUCTION

2.1 BACKGROUND INFORMATION

The first description of PD was published just over 200 years ago by James Parkinson in *Essay on the Shaking Palsy* (Parkinson 1817). Since its original description, the clinical diagnosis of PD has centered on its cardinal motor deficits including bradykinesia, rigidity, and rest tremor (Postuma 2015, Savica 2018). Loss of dopamine-secreting neurons within the substantia nigra and presence of Lewy bodies are the major pathological findings in PD (Connolly 2014). Early in the disease course, dopamine deficiency is the predominant neurochemical abnormality, but as PD progresses, both nonmotor and motor symptoms emerge that are unresponsive to dopaminergic medication (Connolly 2014). Nonmotor manifestations, including cognitive impairment, have a detrimental impact on quality of life and function (Goldman 2011, Svenningsson 2012). In addition, it has become increasingly apparent that PD patients at all stages of the disease can develop cognitive dysfunction (Schneider 2015, Litvan 2011) ranging from mild cognitive impairment to severe dementia.

PD is the second most common neurodegenerative disease behind Alzheimer's disease (AD), with an average age at onset of approximately 60 years (Olanow 2009). An estimated 6.2 million people throughout the world have PD (Dorsey 2018), with 1 million individuals each in the US and Europe (Olanow 2009). Because the incidence of PD increases sharply with age, and the world population is aging, the number of individuals affected is poised for exponential growth; projections indicate the number of people with PD worldwide will double from 6.9 million to 14.2 million in 2040 (Dorsey 2018). In the US, projections indicate that the number of persons living with PD of all types will increase significantly from approximately 866,000 persons in 2015 to 1.96 million by 2060 (Savica 2018). In that time, it is projected that the number of persons living with PDD will increase from 312,000 persons in 2015 to 810,000 by 2060 (Savica 2018).

PD-MCI, defined as subjective and objective cognitive decline that is not normal for age but with no detectable functional impairments, is found in approximately 26.7% of non-demented PD patients and increases with age and duration/severity of PD (Litvan 2011). The majority of PD-MCI cases will convert to PDD over a period of several years, demonstrating that PD-MCI is a risk factor for development of PDD (Janvin 2006, Litvan 2011). The clinical features of PDD include progressive cognitive impairments in attention, executive, and visuospatial functions as well as memory loss (Emre 2007). Hallucinations, delusions, apathy, and mood changes are also frequently associated behavioral features (Emre 2007). Specific criteria for PDD and PD-MCI have been developed by the Movement Disorder Society (MDS) to allow differentiation between MCI and dementia in patients with PD (Emre 2007, Litvan 2012). The defining feature of PDD is that dementia develops in the context of established PD (Emre 2007).

Given its progression and complex, multifaceted disability, the greatest unmet therapeutic need in PD, PD-MCI, and PDD is identification of effective neuroprotective and disease-modifying agents (AIDakheel 2014). Current barriers include limited knowledge of the basic mechanisms of PD, PD-MCI and PDD, and a multitude of challenges in assessment of disease progression and therapeutic efficacy (AIDakheel 2014).

In 2011, data in parabiotic animal models demonstrated that factors found in circulation could affect the aging brain, and that rejuvenating factors from young animals may ameliorate the effects of aging (Villeda 2011). Following these findings, studies were performed to explore the therapeutic effects of systemic exposure of aged mice to young mouse plasma by direct injection (Villeda 2014). Systemic administration of young mouse plasma in aged mice improved age-related impairments in cognition. In addition, the data demonstrated that exposure of aged mice to young mouse plasma counteracts age-related impairment at the molecular and structural levels in the hippocampus (Villeda 2014). These studies lay the foundation for the hypothesis that soluble circulating factors from young human plasma developed from the plasma of donors aged 18-23 years (Young Plasma) may have beneficial effects on cognitive functions in diseases such as Alzheimer's disease and PD (PD-MCI and PDD).

Although fresh frozen plasma from young donors can be tested as a treatment in humans, safer products have been developed based on pooling the plasma from highly selected donations, fractionating them into clearly defined components, and providing additional processing steps to reduce the potential for pathogen transmission. GRF6021 is a human fraction, manufactured by Grifols Therapeutics, Inc., that serves as a viable source of infusible plasma proteins from healthy male and female donors (PI).

Multiple nonclinical studies conducted by Alkahest (see Section 2.2, Rationale) have demonstrated the beneficial effects of GRF6021 in age-related cognitive/motor decline and histopathological endpoints in mouse models.

These studies complemented the findings from the initial studies conducted by Villeda et al (Villeda 2011, Villeda 2014) and confirmed that factors present in human plasma protect against brain aging and ameliorate age-related cognitive and motor impairments in mice, laying the foundation for testing this [REDACTED] fraction in humans experiencing cognitive decline from age-related neurodegenerative diseases.

2.2 RATIONALE

Protocol ALK6021-201 will evaluate GRF6021 administered via IV infusion. Nonclinical studies conducted by Alkahest have demonstrated that both Young Plasma and GRF6021 confer beneficial outcomes in cognitive decline, motor function, neuroinflammation, synaptic density, and neurogenesis in mouse models (ALK-2015-R002, VIV-2016-R003, VIV-2016-R009, VIV-2016-R014, VIV-2016-R020, VIV-2016-R021, VIV-2016-R024, VIV-2017-R025, VIV-2017-R036, VIV-2017-R038, VIV-2018-R069, 2018-CET01, 2018-CRL03, 2018-QPS01).

Initial Alkahest nonclinical studies were performed to test whether the positive effects observed with young mouse plasma could be replicated using Young Plasma. Treatment of aged NODscid (non-obese diabetic severe combined immunodeficiency) mice with Young Plasma (100-150 μ l per injection, two injections per week for 3-5 weeks) resulted in improved cognitive and motor performance in standard behavioral tests (ALK-2015-R002). These cognitive changes were further supported by electrophysiological and histological correlates of enhanced memory. Together, these results provided support for the hypothesis that young human plasma infusions may have functional clinical benefits, potentially ameliorating or halting the progression of age-related cognitive decline.

Subsequent nonclinical studies at Alkahest were performed to test the effects of GRF6021 using various dosing paradigms in NODscid, NSG (NODscid Gamma), C57BL/6J, and Line 61 α -Synuclein (α -Syn) transgenic mice. Initially, mice were dosed with 150 μ L of Young Plasma, GRF6021, or saline (control) via IV infusions 2 times per week for 5 weeks (VIV-2016-R003). A subsequent study examined the same dosing regimen for a period of 23 weeks, to assess the effects of treatment on age-dependent changes in behavioral and cognitive function over a period of approximately 6 months (VIV-2016-R014). Following these studies, a novel dosing regimen for GRF6021 that consisted of one 150 μ L dose every day for 7 consecutive days (referred to as “pulsed dosing”) was assessed, both alone and compared to other intermittent weekly dosing regimens (VIV-2016-R009, VIV-2016-R021, VIV-2016-R024, VIV-2017-R025, 2018-CET-01, 2018-CRL03, 2018-QPS01). Additional studies examined dosing of 150 μ L for 5 consecutive days (VIV-2017-R038) as well as subsequent booster dosing for 5 consecutive days (VIV-2017-R036) which is the pulsed-dosing regimen chosen for ALK6021-201.

These studies demonstrated that pulsed dosing with GRF6021 led to significant improvements in cognitive performance, motor function, and histological correlates. Furthermore, the beneficial effects lasted up to 3 months after the end of dosing, suggesting that continuous repeat dosing may not be required (VIV-2017-R036, VIV-2017-R038). After pulsed dosing with GRF6021 in old mice, there is a well-defined timecourse of effects on the brain. Within hours of the end of dosing, C-fos expression increases, demonstrating that GRF6021 administered intravenously results in neuronal activation (2018-CET01). Over the course of a few days to a few weeks, there is a reduction in age-related neuroinflammation, and an improvement in age-related deficits in cognition and locomotion (2018-CET-01, 2018-CRL03, 2018-QPS01). Lastly, there is an increase in synaptic density and hippocampal neurogenesis; the latter lasts for up to 11 weeks after the end of dosing (VIV-2017-R038). Together, these studies indicate that 5 consecutive days of dosing (“pulsed dosing”) of GRF6021 and cognitive and other testing for a period of 11 weeks thereafter, followed by a second “booster” dosing period is a reasonable study design in human subjects (VIV-2017-R036).

A randomized, double-blind, placebo-controlled study design has been selected to reduce bias in the interpretation of both safety signals and cognitive and motor endpoints. Since this is primarily a safety and tolerability study, a 2:1 randomization ratio was chosen to increase the number of subjects exposed to active GRF6021 and thus provide additional safety data, while at the same time acquiring data on the potential benefits of GRF6021 in individuals with PD and cognitive impairment. Within-subject and between-group cognitive and motor changes associated with the use of GRF6021 will be evaluated.

While the primary objective of this study is safety and tolerability, and the study is not statistically powered to test specific hypotheses regarding changes in cognitive and motor function, the results are expected to provide initial data on the magnitude and variability of beneficial effects on cognitive and motor endpoints and lay the foundation for larger trials designed and statistically powered to characterize the potential benefits of GRF6021 in PD-MCI, PDD, and other neurodegenerative disorders typified by cognitive and motor dysfunction.

The population of individuals with PD-MCI and mild-to-moderate PDD was chosen for this clinical study as they have identifiable deficits in cognitive function with limited treatment options, making them a population for whom the balance of risk to potential benefit of treatment with GRF6021 is reasonable.

The human dose level for this study was selected based on the known safety profile of GRF6021 and scaling from efficacious doses in nonclinical studies. No safety concerns were observed in nonclinical studies using repeated doses of 150 µL in mice.

GRF6021 is a [REDACTED] fraction consisting of multiple proteins with a total concentration of [REDACTED] 100 mL. Dosing of GRF6021 is by IV infusion of specified volumes, thus, using allometric scaling, a dose of 150 µL yields an equivalent human dose using body surface area scaling of 28.4 mL. Allometric scaling is used for small molecules whose elimination is dependent on hepatic metabolism. Alternative scaling methods include mg/kg (recommended for macromolecules >100 kDa) and volumetric scaling based on relative blood volumes. Because GRF6021 contains a complex mixture of proteins with a molecular weight predominantly <100 kDa, and because the beneficial effects of these proteins on cognition are believed to occur in the circulation, the concentration of these proteins per blood volume may be the scaling method most likely to accurately estimate the human potential effective dose.

Using isometric scaling based on blood volume, the mouse dose of 150 µL is equivalent to a human dose of 413 mL, as outlined in Table 1. The dose used in this study is [REDACTED] GRF6021, which is below the equivalent human dose of 413 mL.

Table 1 Isometric Scaling Based on Blood Volume

	Mouse	Human Equivalent Dose (70 kg person)	Human Proposed Dose
GRF6021 Protein Content	[REDACTED]	[REDACTED]	[REDACTED]
Dose Volume	150 µL	413 mL	[REDACTED]
Protein per Dose	[REDACTED] mg	[REDACTED] g	[REDACTED] g
Blood Volume	2 mL	5,500 mL	5,500 mL
Protein per Dose per mL of Blood	[REDACTED] mg/mL	[REDACTED] mg/mL	[REDACTED] mg/mL

Given the [REDACTED] with GRF6021 during which doses of [REDACTED] have been well tolerated, the investigational dose of [REDACTED] of GRF6021 per day for five days represents a reasonable and appropriate dosing regimen for evaluation in this clinical context ([REDACTED], [REDACTED]).

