7.1.1.1.2 Assessment of Parkinson’s Disease and Cognitive Impairment

The diagnosis of PD will be verified using MDS-PD criteria ([Postuma 2015](#))([Appendix 8](#)). The prerequisite to apply the MDS-PD criteria is the presence of parkinsonism, defined as bradykinesia, in combination with either rest tremor, rigidity, or both. These features must be clearly demonstrable and not attributable to confounding factors ([Postuma 2015](#)). The stage of the disease will be classified using the Hoehn and Yahr scale.

Subjects will also be evaluated for PD-MCI (Level I) and PDD based on MDS criteria ([Litvan 2012](#), [Emre 2007](#)). PD-MCI is a syndrome defined by clinical, cognitive, and functional deficits ([Litvan 2012](#))([Appendix 9](#)). The MDS criteria for MCI were developed to address issues relatively specific to PD. The criteria were also designed to be consistent with the MDS proposed PDD criteria ([Emre 2007](#))([Appendix 10](#)) and thereby allow differentiation between MCI and dementia in patients with PD.

Global cognition (a requisite for the diagnosis of PD-MCI Level I) will be assessed using the MoCA ([Nasreddine 2005](#))([Appendix 1](#))(see [Section 7.1.1.3.1](#)). The score range for PD-MCI is 19-25.2, and for PDD it is 11.4-21. While the score ranges overlap, differentiation between the conditions is dependent upon associated functional impairment ([Doerflinger 2012](#)). Per the inclusion criteria for this study, subjects must have a MoCA score of 13-25, inclusive (see [Section 5.1 Inclusion Criteria](#)).

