10.4.8 ADDITIONAL SUBGROUP ANALYSES

Not applicable.

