10.5 SAMPLE SIZE

A total of approximately 90 subjects will be randomized in a 2:1 ratio to active treatment (approximately 60 subjects) or placebo (approximately 30 subjects), with the intent of obtaining ~68 evaluable subjects who have received at least 5 doses and completed the study through Visit 8. Subjects who discontinue prior to completing Visit 8 may be replaced. Subjects who withdraw or are withdrawn during screening will be replaced.

The study is not statistically powered to detect differences in measures of clinical efficacy or biomarker endpoints. To evaluate potential safety signals, the statistical approximation described by Hanley (aka the “Rule of Threes” in which the upper bound of the 95% confidence interval for the frequency of an unreported AE is at most $3/n$ % where n represents the number of subjects who received active GRF6021 in the study) will be used. In a sample of 60 subjects, the upper bound of the 95% confidence interval for the frequency of an unobserved

AE is approximately 5%. In addition, the proposed sample size may be sufficient to identify trends in efficacy endpoints that will be used to determine the appropriate sample size for subsequent studies.

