8.2.1. Montreal Cognitive Assessment (MoCA)

The MoCA is a 1-page, 30-point test designed as a rapid screening instrument for mild cognitive dysfunction. The questionnaire assesses several different cognitive domains, including attention and concentration, executive functions, memory, language, visuospatial skills, conceptual thinking, calculations, and orientation. Higher scores indicate better cognitive function; the total possible score is 30 and a score of 26 or more is considered normal. Derivation for the MoCA total score is described in Section 6.1.7.

The MoCA will be collected at Screening (Visit 1), Week 4 (Visit 9), and Week 16 (Visit 17).

Change from baseline to study visit in the MoCA total score and individual domains will be summarized by treatment group. Boxplots of the MoCA total score will also be provided by treatment group and visit. A test of hypothesis comparing mean total scores between baseline and subsequent study visits will be conducted using a 2-sided paired t-test or Wilcoxon signed

rank test, as appropriate. The null hypothesis is that the change from baseline to subsequent visit is 0.

Additionally, the mean change from baseline in MoCA total score will be compared between treatment groups using an ANCOVA model with treatment, visit, and treatment by visit interaction as a main effects and baseline MoCA total score, age, and ApoE genotype as covariates.

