11.1. Hoehn and Yahr Scale

The Hoehn and Yahr Scale is used to describe the symptom progression of PD. The scale is as follows:

Stage	Description
0	No signs of disease
1.0	Symptoms are very mild; unilateral involvement only
2	Bilateral involvement without impairment of balance

Stage	Description
3	Mild to moderate involvement; some postural instability but physically independent; needs assistance to recover from pull test
4	Severe disability; still able to walk or stand unassisted
5	Wheelchair bound or bedridden unless aided

The Hoehn and Yahr Scale will be assessed at Screening (Visit 1) only and will be listed.

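### The screening diagnosis of PD-MCI or PDD enters no between-arm model, baseline table or efficacy summary in the SAP, so an imbalance between arms is only partly visible and not directly adjusted for

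*Protocol*

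**What the plan says.** Protocol 2.2 expects "initial data on the magnitude and variability of beneficial effects on cognitive and motor endpoints" and intends the results to "lay the foundation for larger trials designed and statistically powered to characterize the potential benefits of GRF6021 in PD-MCI, PDD", with other neurodegenerative disorders named after them. Protocol 10.5 adds that "the proposed sample size may be sufficient to identify trends in efficacy endpoints" and that these trends will help size subsequent studies.

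Either diagnosis is eligible, and Protocol 7.3.1 has the site verify PD-MCI or PDD at Visit 1. Protocol 7.1.1.1.2 describes two overlapping groups: "The score range for PD-MCI is 19-25.2, and for PDD it is 11.4-21". It says that functional impairment is what tells them apart.

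How the plan treats the diagnosis afterwards:

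- **Randomisation** (Protocol 10.6.1, SAP 3.5): stratified by sex only.
- **Models** (SAP 8.2): MoCA has "baseline MoCA total score, age, and ApoE genotype as covariates". D-KEFS, CISI-PD, PDQ-39 and dCDT follow the same pattern. MDS-UPDRS has baseline score and age only. The SE-ADL comparison is a CMH test with no diagnosis stratum.
- **Baseline table** (SAP 7.3, Table 14.1.2): tests demographics, height, weight, disease duration and ApoE genotype between arms, but not diagnosis.
- **Hoehn and Yahr** (SAP 11.1): "will be assessed at Screening (Visit 1) only and will be listed".
- **Subgroups** (Protocol 10.4.8): "Not applicable".
- **History** (Table 14.1.3.2): tabulates histories of PD-MCI and PDD by arm in the Safety Set, through four coded lower-level terms.

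Diagnosis also serves as a membership test for the Evaluable Set (Protocol 10.3) and the Per Protocol Set (SAP 5). Neither use separates PD-MCI from PDD.

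**The concern.** Diagnosis is a baseline factor assessed before randomisation, and the protocol itself treats the two groups as different in cognition and function. If it predicts change over 24 weeks, an unequal share between arms shifts the treatment comparison. SAP 7.3 tests baseline variables to judge whether randomisation gave comparable groups, and SAP 6.1.2 allows a variable that differs to be added to the models. A variable that is never tabulated or tested will not reliably reach that rule.

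The second stake is interpretation. A reader planning a later study receives one pooled change and one pooled SD, with nothing to show whether either describes PD-MCI, PDD or both.

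**Working it through.** **Inputs from the documents.** About 90 randomised 2:1; 25% drop-out; about 68 evaluable (Protocol summary and 10.5). Check: 90 × 0.75 = 67.5, which agrees. Split 2:1, this is 45 active and 22.5, taken as 23, placebo.

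**Not in the documents, so assumed.** The PD-MCI/PDD split, the SDs and the effects by diagnosis. Ranges are shown.

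**1. Chance imbalance in diagnosis.** Treat the PDD count in each arm as binomial with share p, and sum the exact probability that the two arm proportions differ by at least the stated amount.

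| Arms | PDD share | 15 points or more | 20 points or more |
|---|---|---|---|
| 45:23 | 50% | 23% | 12% |
| 45:23 | 30% or 70% | 19% | 9% |
| 60:30 | 50% | 21% | 9% |

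**2. What an imbalance would do.** If mean change differs between diagnoses by 0.3 to 0.6 SD (assumed), a 20-point imbalance shifts an unadjusted difference by 0.20 × 0.3 = 0.06 SD to 0.20 × 0.6 = 0.12 SD. The standard error of the difference is √(1/45 + 1/23) = 0.256 SD, so the shift is 0.23 to 0.47 of a standard error. The planned models are not unadjusted: baseline score and age take up part of this, and how much cannot be derived from the documents.

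**3. Whether the pooled effect suits both diagnoses.** The pooled effect is w·d(PD-MCI) + (1 − w)·d(PDD), where w is the PD-MCI share. For a later 1:1 trial at two-sided 0.05 and 80% power, n per arm = 2(1.96 + 0.842)²/d² ≈ 15.7/d².

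- Equal effects of 0.5 SD: the pooled effect is 0.5, so 15.7/0.25 gives 63 per arm for either diagnosis. Pooling does no harm.
- Effects of 0.6 (PD-MCI) and 0.2 (PDD), with w from 0.3 to 0.7: the pooled effect is 0.32 to 0.48, so 154 to 69 per arm, against 44 for PD-MCI and 393 for PDD.

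The planned outputs cannot tell these two cases apart.

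**4. What a split by diagnosis could show.** The 95% CI half-width for a treatment difference, in SD units, is t(0.975, df) × √(1/n₁ + 1/n₂).

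| Share of the diagnosis | n active : placebo | Half-width |
|---|---|---|
| All subjects | 45 : 23 | 0.51 |
| 70% | 31.5 : 16.1 | 0.62 |
| 50% | 22.5 : 11.5 | 0.74 |
| 30% | 13.5 : 6.9 | 0.98 |

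SDs are also imprecise. With 11 subjects, the 95% interval for an SD runs from 0.70 to 1.75 times the estimate, which changes a planned N by a factor of 0.49 to 3.1. With 22 subjects the factor for N is 0.59 to 2.0.

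**The case against.** The strongest reply is one of proportion. The primary objective is safety, efficacy is unpowered and mainly descriptive, and planning no subgroup analysis is defensible with about 68 evaluable subjects. Step 4 supports this: cells of about 11 to 22 cannot reliably size separate later trials. That stands, and it limits the remedy to description.

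A second reply is that imbalance is not invisible. SE-ADL at baseline is tabulated by arm with a P value, and function is what separates the diagnoses. Baseline MoCA, MDS-UPDRS and the CISI-PD disability and cognitive items also appear by arm. This stands in part. These are proxies: the MoCA ranges overlap from 19 to 21, and none of these measures reproduces the verified diagnosis. Table 14.1.3.2 is a planned summary that touches on diagnosis, so it would be wrong to say that none exists. But its terms do not map cleanly onto PD-MCI, a subject can count under several of them, and nothing is crossed with outcome.

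Stronger readings are tempting and are not supported. A reader might infer that pooled estimates fit neither population, or that the pooled SD is too large for one diagnosis and too small for the other. Both need heterogeneity that the documents do not report. A reader might also infer a promise of a separate trial in each diagnosis. The rationale only lists possible targets, and for a later trial enrolling the same mix the pooled SD is the right input.

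**Conclusion.** The concern holds in limited form. The supplied SAP leaves a prognostically plausible factor, assessed before randomisation, out of its between-arm models, its baseline comparison and its efficacy summaries. Assuming half the subjects have PDD, an imbalance of 15 points or more has about a 23% chance (19% at a 30% or 70% share). Under the assumed differences in step 2, a 20-point imbalance moves an unadjusted estimate by less than half a standard error. That is worth removing, but it would not by itself overturn a result. The exposure is greatest for MDS-UPDRS, whose model has no covariate beyond baseline score and age.

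Whether pooling misleads later planning cannot be settled from the documents; the fault is that the plan would not show it either way. The finding does not extend to CDR-CCB, whose analysis plan is separate and not shown, and it does not touch the primary safety objective.

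**What to change.** 1. Add the screening diagnosis (PD-MCI or PDD) as a covariate in the between-arm models of SAP 8.2. This costs one degree of freedom per model and overlaps somewhat with baseline MoCA.
2. Add a diagnosis row by arm to Table 14.1.2. A Hoehn and Yahr row is optional.
3. Add one descriptive table giving n, mean and SD of change by arm within diagnosis for MoCA and MDS-UPDRS Part 3. Give no P values. Note under it that 95% CI half-widths for a treatment difference within one diagnosis are about 0.6 to 1.0 SD, and that the cells are too small to size later trials alone.

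The cost is SAP wording, one table row and one table. No new assessment is needed, since the diagnosis is verified at Visit 1. However, neither document shows the case report form, and no planned listing carries the diagnosis outside medical history. Confirm that it is held as a data field; if it is not, take it from the screening source records before unblinding.
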